## **2. LIST OF ABBREVIATIONS**

ADR	Adverse Drug Reaction
AE	Adverse Event
CAT	COPD Assessment Test
COPD	Chronic Obstructive Pulmonary Disease
CRF	Case Report Form
eCRF	Electronic Case Report Form
EDC	Electronic Data Capture
EU-QPPV	European Union – Qualified Person for Pharmacovigilance
FDC	Fix Dose Combination
FEV 1	Forced Expiratory Volume in one second
FVC	Forced Vital Capacity
GPSP	Good Post- marketing Study Practice
ICS	Inhaled Corticosteroid
IRB	Institutional Review Board
J-PAL	Japanese Law for Ensuring the Quality, Efficacy, and Safety of Drugs and Medical Devices
J-RMP	Japan Risk Management Plan
LABA	Long Acting Beta2 Agonist
LAMA	Long Acting Muscarinic Antagonist
MedDRA	Medical Dictionary for Drug Regulatory Activities
PMDA	Pharmaceuticals and Medical Devices Agency
PMS	Post Marketing Surveillance
SAE	Serious Adverse Event

### **3. RESPONSIBLE PARTIES**

Contact details and the list of all investigators will be kept in a stand-alone document. This document will be managed in the PMS tracking system which manage the contracts with site and investigators name.

**4. ABSTRACT**

Name of company: Boehringer Ingelheim			
Name of finished medicinal product: Spiolto Respimat 28 puffs/ Spiolto Respimat 60 puffs			
Name of active ingredient: Tiotropium + olodaterol fixed-dose combination solution for inhalation - RESPIMAT			
Protocol date: 15 November 2015	Study number: 1237.34	Version/Revision: Ver 2.0	Version/Revision date: 10 MAY 2016
Title of study:	Post Marketing Surveillance (PMS) on long-term use of tiotropium+olodaterol fixed dose combination (Tio+Olo FDC) 5µg /5µg in patients with chronic obstructive pulmonary disease (chronic bronchitis, emphysema) in Japan		
Rationale and background:	The number of patients exposed to Tio+Olo FDC 5µg /5µg is limited in clinical trials. In addition, the clinical trial setting had some limitations compared to the real-world setting, such as inclusion/exclusion criteria defined patient's background and restriction of concomitant medications. In addition it is important to understand treatment patterns in routine clinical practice.		
Research question and objectives:	The study objective is to assess the long-term safety and effectiveness of Tio+Olo FDC 5µg/5µg in patients with chronic obstructive pulmonary disease (chronic bronchitis, emphysema) in real-world setting.		
Study design:	Observational study based on newly collected data for 52 weeks.		
Population:	
 
- Inclusion criteria 
 
• Patients who have been diagnosed with chronic obstructive pulmonary disease (chronic bronchitis, emphysema) by physician and need to be treated co-administration of a long-acting inhalational anticholinergic and a long-acting inhalational β2-agonist to relief of various symptoms associated with the obstructive impairment of airways.
 
• Patients who are prescribed Tio+Olo FDC 5µg /5µg for the first time
 
 
 
- Exclusion criteria 
 
• Patients who have already been registered in this study once (re-entry of patients is not allowed)
 
• Patients who are participating in a clinical trial or registry.
 
• Patients who have a contraindication to Tio+Olo FDC 5µg /5µg
 
 
 
		

	defined in the package insert for Tio+Olo FDC 5µg /5µg.
Variables:	
Baseline characteristics
 
Demographics
 
Duration from indication
 
COPD status (severity (i.e. GOLD stage))
 
Tio+Olo FDC 5µg /5µg administration status
 
Medical history/ baseline conditions
 
Previous /concomitant therapies
 
Concomitant/ past medications (start/stop date, dosage, unknown)
 
Chronic obstructive pulmonary disease (chronic bronchitis, emphysema) medications (ICS, LABA, LAMA, other, unknown)
 
other medications (start/stop date, dosage, unknown)
 
CAT (COPD Assessment Test)
 
FVC and FEV1 (if the data is available at sites with information of pulmonary medication (i.e. pre-dose or post-dose))
 
Pregnancy

Data sources:	Patients' data will be collected by electronic Case Report Form (eCRF) on EDC system
Study size:	1000 (safety set)
Data analysis:	Analyses are descriptive in nature. AEs are described with their incidence and incidence rate per treatment time. Subgroup analyses are performed for suitable sized samples with regard to patient characteristics and AE groups of medical interest. Due to the nature of the observational study, no confirmatory statistical testing is foreseen in this study.
Milestones:	
Study Report planned to be archived in 3Q 2019
 
Study result based on study report is submitted in the re-examination document to PMDA in 4Q 2023.

## 5. AMENDMENTS AND UPDATES

Number	Date	Section of study protocol	Amendment or update	Reason
2.0	10 MAY 2016	Abstract	Change the indication	To comply with J-PI
		Milestones	Change the study period	Delay of EDC system setup
		Physicians' global assessment	Add "( compared to the day before initiation of Tio+Olo FDC 5µg /5µg)"	To make the rule clearer
		Data management	Change name of CRO	CRO changed their name
		9.1 STUDY DESIGN	Updated	Added visits based on the requirement from PMDA.

## **6. MILESTONES**

Milestone	Planned Date
Start of data collection	23 August 2016 (Launch of the investigated product: 3 December 2015)
End of data collection	30 November 2018
Registration in the EU PAS register	To be registered
Final report of study results:	July 2019

## 7. RATIONALE AND BACKGROUND

This PMS study is planned according to the requirement by the Pharmaceutical Affairs Law in Japan (J-PAL). The law requires in principle that data on the safety and effectiveness of all launched products to be accumulated under real-world clinical practice.

The data collected in the PMS study are required to be submitted to the Pharmaceuticals and Medical Devices Agency (PMDA), the local regulatory agency in Japan, according to the process of re-examination which will take place 8 years after approval of registration. The PMS study is a part of the local Risk Management Plan in Japan (J-RMP) to be submitted to PMDA at New Drug Application.

The results of clinical trials and PMS studies related to Tio mono or Tio+Olo FDC are summarised below.

Clinical trials evaluating Tio mono until re-examination:

Until now, there were five clinical trials [P05-08673][U03-3113][U03-3144][U08-3718][P09-15298] in Japanese patients with COPD for Tio HandiHaler and Tio Respimat as indicated in Table 7: 1.

Table7: 1 Study list of Tiotropium mono until re-examination

Study type [reference], BI study number	Treatment period	Number of Japanese patients (safety set)
Phase II, dose finding study [P05-08673], 205.139	Single dose	HandiHaler, 27
Phase III, DBT [U03-3113], 205.226	4 weeks	HandiHaler, 67
Phase III for long term administration, open trial for safety [U03-3144], 205.227	1 year	HandiHaler, 110
Phase IIIb, UPLIFT trial [U08-3718], 205.235	4 years	HandiHaler, 100
Phase II, crossover trial for equivalence between HandiHaler and Respimat [P09-15298], 205.291	4 weeks	HandiHaler, 81 Respimat, 76

A total of 385 Japanese patients received Tio in these clinical trials. Even though there were no reports of safety concern to Tio in patients with COPD based on the results of clinical trials, PMDA directed to conduct PMS to fulfil regulatory obligations established as a condition of marketing approval. Therefore two PMS studies [U09-1849-01] [U09-2234-01] for Tio HandiHaler and 1 PMS study [U12-2679-01] for Tio Respimat were conducted. A total of 4130 patients received Tio in these PMS studies.

Clinical trials evaluating Tio+Olo FDC:

A total of 238 Japanese patients were treated with Tio+Olo FDC (5µg/ 5µg; the planned registered dose) up to 52 weeks in 3 phase III trials for Tio+Olo FDC program [U13-1759-01][U13-1760-01] [U13-1762-01]. Clinical trials of Tio+Olo FDC also include 149 Japanese patients receiving Olo mono 5µg and 76 Japanese patients receiving Tio mono 5µg.

There were no safety concerns of Tio+Olo FDC, Olo mono and Tio mono in these clinical trials in Japanese patients compared to the respective global safety experience. However, clinical trials have limitations in comparison to real-world clinical practice due to the restriction of concomitant drugs and the exclusion of complicating severe diseases. In addition, no safety experience beyond 1-year of exposure is currently available from clinical trials with Tio+Olo FDC

Therefore, PMDA directed to conduct PMS to collect mainly safety data from real-world clinical practice to fulfil regulatory obligations established as a condition of marketing approval.

### **Japanese regulation related to Post Marketing Surveillance (PMS)**

This PMS study is planned according to the Japanese Law for Ensuring the Quality, Efficacy, and Safety of Drugs and Medical. The law requires in principle that data on the safety and effectiveness of all launched products to be accumulated under real-world clinical practice. The data collected in the PMS study are required to be submitted to the Pharmaceuticals and Medical Devices Agency (PMDA), the local regulatory agency in Japan, according to the process of re-examination which will take place 8 years after approval of registration. The PMS study is a part of the local Risk Management Plan in Japan (J-RMP) to be submitted to PMDA at New Drug Application.

## **8. RESEARCH QUESTION AND OBJECTIVES**

This PMS study is one of the action plans of collecting post-marketing safety information focused on the following risks and information of Tio+Olo FDC 5µg/5µg in the J-RMP.

- Important identified risks: Cardiac failure, atrial fibrillation and extrasystoles, Ileus, Angle closure glaucoma, Anaphylaxis
- Important potential risks: Cardiac disorder (Myocardial ischaemia, Cardiac arrhythmia), Intubation and mortality related to asthma
- Important missing information: none specified

The study objective is to assess the long-term safety and effectiveness of Tio+Olo FDC 5µg/5µg in patients with chronic obstructive pulmonary disease (chronic bronchitis, emphysema) in real-world setting.

## **9. RESEARCH METHODS**

### **9.1 STUDY DESIGN**

This is an observational study based on newly collect real-world data (i.e., data under real-world practice) to evaluate safety and effectiveness of Tio+Olo FDC 5µg/5µg in patients with chronic obstructive pulmonary disease (chronic bronchitis, emphysema).

The study will be initiated after marketing of Tio+Olo FDC 5µg/5µg in Japan. The study will consist of a baseline visit and further visits in a 52-week follow-up for patients who have initiated the Tio+Olo FDC 5µg/5µg treatment.

As this is an observational study, no specific treatment is mandated or withheld from the patients. The choice of maintenance treatment for chronic obstructive pulmonary disease (chronic bronchitis, emphysema) must be according to regular medical practice and at discretion of physician (i.e., no randomised assignment of patient to treatment [Tio+Olo FDC or other treatment] is performed). In total, approximately 1100 patients are planned to be registered at approximately 200 study sites in the study.

Patients participating in the subsequent follow-up will undergo regular observations. These observations should be reported after 4, 12, 24 and 52 weeks since the initiation of Tio+Olo FDC 5µg/5µg as long as they continue to receive the treatment. Patients will not be followed any longer once they are reported to have discontinued the Tio+Olo FDC 5µg/5µg treatment. Patients who experience adverse events will be followed up until detailed information on the outcome of the adverse event is collected.

The primary outcome of this study is the incidence and exposure-time adjusted incidence rate of adverse drug reactions (ADRs).

The secondary outcome of this study is:

- COPD assessment test (CAT) at 12 weeks.

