#### **9.4 DATA SOURCES**

Case Report Forms (CRFs) for individual patients will be provided by the sponsor via the Electronic Data Capture (EDC) system.

In EDC system, two casebooks will be set up; Book 1 includes baseline, 4 weeks, and 12 weeks. Book 2 includes 24 weeks and 52 weeks.

The data are to be transmitted immediately after being entered into EDC at 12 weeks (Book 1) and 52 weeks (Book 2) after the start of treatment or at discontinuation.

For any adverse events, the data should be immediately entered into EDC and transmitted.

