### 9.7.2 Analyses of Safety

The safety analysis will include all patients registered in the study and receiving the Tio+Olo FDC 5µg/5µg treatment except for patients who meet the ineligible criteria (see section 9.7). In general, safety analyses will be descriptive in nature, be based on BI standards, and focus on AEs related to the Tio+Olo FDC 5µg/5µg treatment.

AEs will be coded using the current version of the Medical Dictionary for Drug Regulatory Activities (MedDRA) and will be based on the concept of treatment emergent AEs. To this end, all AEs occurring between the initiation of Tio+Olo FDC 5µg/5µg prescribed at baseline visit and 21 days (inclusive) after the last administration will be considered 'treatment emergent'. An AE is considered to be an ADR if either the physician/investigator who has reported the AE or the sponsor assesses its causal relationship as 'related'.

The incidence (n and % in treatment group) and treatment exposure time adjusted incidence rate (n in 100 patient years) of AEs in patients treated with Tio-Olo FDC (treatment emergent including 21 days after discontinuation of Tio+Olo FDC medication) will be tabulated by MedDRA SOC and PT for overall and for subgroups based on the important baseline characteristics, if sample size allows (see 9.3.3)

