### Collection and Reporting of AEs:

The study design is of non-interventional nature and the study is conducted within the conditions of the approved marketing authorization. Sufficient data from controlled interventional trials are available to support the evidence on the safety and efficacy of the studied BI drug. For this reason the following AE collection and reporting requirements have been defined.

The following must be collected by the investigator in the (e) CRF via EDC system from first intake of Tio+Olo FDC 5µg/5µg prescribed at baseline visit and within 21 days (inclusive) after the last intake:

- all AEs (serious and non-serious) as soon as possible,
- all AEs with fatal outcome in patients exposed to Spiolto Respimat as soon as possible,
- all AEs which are relevant for a serious ADR or an AE with fatal outcome in patients exposed to Spiolto Respimat as soon as possible

All ADRs including those persisting after study completion must be followed up until they are resolved, have been sufficiently characterized, or no further information can be obtained.

The investigator carefully assesses whether an AE constitutes an ADR using the information below.

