6. GENERAL ANALYSIS DEFINITIONS

6.1 TREATMENT(S)

For basic information on treatment in the study, please refer to NIS Protocol Section 4. The technical specification for treatment set-up is described in the Analysis Data Set (ADS) plan.

For safety analyses, data up to 21 days after last treatment intake during observation period will be considered as on treatment for AE.

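### Protocol 9.1 ends follow-up when discontinuation is reported, but adverse events are required and analysed to 21 days after the last dose, so new events in that window may be under-collected

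*Protocol*

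**What the plan says.** Three places in the protocol end observation at discontinuation:

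- **9.1 Study design:** "Patients will not be followed any longer once they are reported to have discontinued" the study treatment. The next sentence makes an exception: "Patients who experience adverse events will be followed up until detailed information on the outcome of the adverse event is collected". That covers following a known event to its outcome. It does not set up a search for new events.
- **Annex 2:** adverse events are recorded throughout the observation period. The last column is week 52 or discontinuation, and nothing is scheduled later.
- **9.4 Data sources:** the first casebook is sent at 12 weeks and the second at "52 weeks (Book 2) after the start of treatment or at discontinuation".

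Four places run 21 days longer:

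- **Protocol 11.2:** the investigator must collect all adverse events from first intake and "within 21 days (inclusive) after the last intake".
- **Protocol 9.7.2:** events from the start of treatment to "21 days (inclusive) after the last administration will be considered" treatment emergent.
- **SAP 6.1:** "data up to 21 days after last treatment intake during observation period" count as on treatment.
- **SAP 7.8.1:** the same window is used for the adverse event analyses.

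The primary outcome (9.1) is both the incidence and the exposure-adjusted incidence rate of adverse drug reactions. Exposure for the rate ends at the last administration or final contact (Protocol 9.3.1), or at last intake minus first intake plus one day (SAP 5.4). Neither adds the 21 days.

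**The concern.** A site that works from the design section and the flow chart closes the patient when discontinuation is reported. A site that works from Section 11 keeps collecting for 21 days after the last dose. About 200 sites may resolve this differently.

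An unobserved window then looks the same as an event-free one. No planned output shows how many discontinued patients have adverse event information to day 21. Protocol 9.10.1.5 rules out direct access to source data, so the sponsor cannot look for missed events there.

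The window feeds the primary outcome, and also serious events, fatal events and the priority cardiovascular items. Protocol 9.3.2 stratifies by prior treatment and age, and SAP 7.8.1 plans odds ratios for reactions by subgroup. If stopping differs between subgroups, completeness of collection may differ too.

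**Working it through.** **1. The plan's own figures.** The documents give no figure for events after discontinuation and no discontinuation rate. The sample-size figures in Protocol 9.5 reproduce but do not bear on this point. The required size is [1.960·√(0.026·0.974) + 2.054·√(0.052·0.948)]² / 0.026² = 872.3, rounded up to 873. The Wilson widths at 1000 patients are 2.00% and 2.77%. Only the 2.6% is used below, for scale.

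**2. Does any text settle the conflict?** Set side by side:

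| Question | Protocol 9.1, 9.4, Annex 2 | Protocol 11.2, 9.7.2; SAP 6.1, 7.8.1 |
|---|---|---|
| When does observation end? | Reported discontinuation | 21 days after last intake |
| Is a contact planned in the 21 days? | No | None specified |
| Can an event be entered then? | Yes, 9.4 asks for immediate entry of any event | Yes, 11.2 requires it |

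The SAP limits its window to the observation period. Annex 2 ends that period at discontinuation, so the phrase does not say which rule applies.

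**3. Size of the window against on-drug time.** Assumptions, not in the documents: a share d of patients stops early, stops are spread evenly over one year, and the full 21 days goes unobserved for every stopper. Taking the 1000 patients of Protocol 9.5:

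- Window = 1000·d·21/365.25 patient-years
- On-drug time = 1000·(1 − d/2) patient-years

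| d | Window | On-drug time | Ratio |
|---|---|---|---|
| 20% | 11.5 | 900 | 1.3% |
| 30% | 17.2 | 850 | 2.0% |
| 40% | 23.0 | 800 | 2.9% |

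The ratio does not depend on the number of patients.

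**4. Other stopping patterns.** If all stoppers stop at day T, the window's share of cohort risk time is d·21 / [d·T + (1 − d)·365 + d·21].

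- Lowest case tried (d = 10%, T = 168): 2.1/347.4 = 0.6%.
- Highest case tried (d = 50%, T = 28): 10.5/207 = 5.1%.

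For a single stopper the share is 21/(T + 21): 43% at day 28, 20% at day 84 and 11% at day 168.

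**5. Direction.**

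- *Incidence proportion:* a missed first event removes a patient from the numerator and leaves the denominator unchanged, so the proportion can only fall.
- *Rate:* let the true event rate be a constant λ, on-drug time T and window time W. With full collection the plan computes λ(T + W)/T = λ(1 + W/T), which is 1.3% to 2.9% too high on the ratios in step 3. With nothing collected in the window it computes λ. Under-collection therefore offsets the mismatch at a constant rate. If events cluster after stopping, the result depends on how strongly.

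**6. Scale in patients.** Protocol 9.5 takes 2.6% with serious cardiovascular events, which is 26 of 1000. At a constant rate, 2.9% of 26 is about 0.75 patients. The planned interval width of 2.0 percentage points is about 20 patients.

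**The case against.** The best defence is that the protocol already covers the window. Section 11.2 is mandatory, and 9.3.2 names Section 11 as the place that governs how events are assessed and reported. Section 9.4 asks for any event to be entered at once, so entry is not tied to casebook transmission. The 9.1 sentence follows the list of regular observations at 4, 12, 24 and 52 weeks, and can be read as ending those only. Follow-up also ends when discontinuation is reported, and that may be after some or all of the 21 days have passed. A reaction that caused the stop would usually be known by then.

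Most of this stands. It means under-collection is a risk and not a certainty, and that charging the full 21 days to every stopper overstates the loss. It does not remove the conflict: a duty and an entry route do not create an occasion on which a new event would be found, and 9.1 as worded still tells sites to stop.

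Three stronger readings are tempting, and the documents do not support them:

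- *That these events will be missed.* 11.2 requires their collection.
- *That the 21 days are counted as observed time.* They enter no exposure denominator in Protocol 9.3.1 or SAP 5.4.
- *That the whole primary outcome is biased downward.* This follows for the incidence proportion only.

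**Conclusion.** The contradiction is real and touches the primary outcome. New events in the 21 days after the last dose may be under-collected, because 9.1 ends follow-up and no later contact is specified.

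At cohort level the effect is modest if the event rate is constant: at most about 1.3% to 2.9% of on-drug time with 20% to 40% stopping evenly over the year, and 0.6% to 5.1% of risk time over the wider stopping patterns tried. It would be larger if events cluster around stopping, but the documents give no figure for that or for the discontinuation rate. For a patient who stops early, the window is a substantial part of the time at risk.

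The mismatch between the numerator and denominator of the rate is a separate defect. It holds even if collection is complete. The correction is cheap enough that both should be put right.

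**What to change.** Reconcile the protocol text with the window it already analyses:

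- **Protocol 9.1:** state that scheduled observations end at discontinuation, and that adverse event collection continues to 21 days after the last intake, as in 11.2.
- **Protocol Annex 2:** make the adverse event row say the same.
- **SAP 6.1 and 7.8.1:** make clear that the reference to the observation period does not cut the 21 days short.
- **SAP 7.8.1:** report how many discontinued patients have adverse event information to day 21.
- **SAP 5.4 and 7.8.1:** either align the rate denominator with the event window or state that the numerator covers 21 days that the denominator leaves out.

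The casebook need not be held until day 21, since 9.4 already allows event entry at any time. Holding it would add a step for each discontinued patient that 11.2 does not require.

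The cost is minor wording and reporting work, and possibly one eCRF item to record the date to which adverse event status is known. No treatment decision is affected.

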## **9.2 SETTING**

### **9.2.1 Site selection:**

Tio+Olo FDC 5µg/5µg has been delivered to the sites and PMS Director who is assigned on Good Post- marketing Study Practice (GPSP) will decide sites to participate in the study based on the site selection checklist.

Planned number of site: Approximately 200 Sites

A medical representative will explain the objective and design of this study to investigators at each study site and exchange a written contract with the head of the study site (e.g., hospital director).

